#### Specific Aims of the Vanderbilt Epicenter Research Plan:

The proposed Vanderbilt Epicenter research plan outlined below is designed to examine several important issues surrounding pathogen transmission, use and misuse of PPE, and methods to improve the protection of HCP and their patients. The proposed studies also harness Vanderbilt's expertise in the use of simulation training and tools (Aim I), monitoring and feedback of practice compliance using a model of shared accountability (Aim II), and the performance of quasi-experimental studies of infection prevention interventions in an operational setting (Aim III). Successful completion of the proposed studies will improve the capacity to prevent and control the spread of EVD, MDROs, *C. difficile* and other infectious pathogens with similar modes of transmission in healthcare settings, thereby helping to prevent and control both current and future outbreaks.

**Specific Aim I:** To examine risk factors for HCP self-contamination with the donning, use, and doffing of PPE used for Contact, Droplet, and EVD-Specific Precautions using simulation laboratory techniques.

**Specific Aim II:** To evaluate in a variety of clinical care settings the effectiveness of a standardized PPE compliance auditing tool coupled with a tiered accountability framework.

**Specific Aim III:** To investigate the impact of preemptive Contact Precautions for residents of long-term care facilities admitted to acute care units, including the impact on the rate of hospital acquisition of MDRO and C. difficile and unintended consequences (e.g. frequency of HCP contacts, patient falls) due to this isolation strategy.

Specific Aim I: To examine risk factors for HCP self-contamination with the donning, use, and doffing of PPE used for Contact, Droplet, and EVD-Specific Precautions using simulation laboratory techniques.

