In a follow up investigation, this team examined compliance with isolation practices among 24 nurses using a simulated patient care setting. Using methods similar to those noted above, poor compliance with PPE donning, in-room PPE use, and PPE doffing was noted. Example breaches included failure to tie gowns at the neck, touching of the face or other nonprotected areas with contaminated gloves, and failure to doff PPE as per recommendations.

Casanova *et al* compared the use of single vs. double gloving while performing a vital signs assessment on a simulation manikin and the risk of MS2 nonpathogenic bacteriophage contamination of the PPE components and participant hands. Among the 18 HCP volunteers, hand contamination with MS2 was significantly more frequent with the use of a single pair of gloves (occurring in 78% of volunteers vs. only 28% of volunteers when double gloving was utilized, *p* = 0.006). Errors in PPE removal were frequent in both scenarios (72% with any error in double gloving scenarios; 67% in the single gloving scenario). Importantly, contamination occurred even with a visible PPE removal protocol present for reference during the scenario, suggesting the need for additional strategies to improve compliance along with these "just-in-time" reminders.

Lai *et al* examined the risk of contamination with different glove removal techniques using a fluorescent solution. Glove removal using any technique led to environmental contamination. Wong and colleagues identified a variable risk of HCP contamination between different types of PPE (gowns or aprons) using simulated respiratory secretion exposure with a fluorescein solution. A randomized crossover study of 50 subjects wearing novel respiratory pathogen precautions PPE (gloves, gown, N95 particulate respirator, face shield, and hair cover with and without a powered air-purifying respirator [PAPR]) also used fluorescein solution to assess contamination with PPE use. The solution was atomized onto the HCP while in the PPE,

[figure not shown]
mimicking exposure to respiratory droplets. Contamination was greater in those who did not wear the PAPR, with the anterior neck, forearms, wrists and hands the most common areas of contamination.

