communication skills and the mitigation of human error in the delivery of patient care. We aim to assess the frequency of and risk factors for PPE breaches using a larger study population and more complex scenarios that mimic typical patient care activities during which PPE is used.

**INNOVATION:** The main innovation of this study Aim is that the majority of prior studies were on single evaluations of PPE breaches (double vs single gloves as example), where the current study will be comprehensive and employ longer and more complex scenarios that mirror actual HCP activities. In addition, 3 different precaution scenarios will be assessed. We will also use a cohort of HCP that is larger than in published investigations of this issue. We believe that patient care settings will not provide this opportunity because such activities usually occur in time-pressed, uncontrolled environments where patients must take precedence. Simulation has been

widely touted as a tool to improve clinical care and patient safety. It is a broad construct that ranges from role-playing to full-scale manikin-based Realistic Patient Simulation (RPS) and includes standardized patients (SP) and partial task trainers of varying sophistication. Realistic Patient Simulations can involve fully interactive simulation environments containing all clinical equipment and cues found in the patient care environment. The manikin to be used in this project (SimMan™) is a computer-controlled plastic patient that generates or emulates physiological findings (e.g. ECG, invasive and non-invasive blood pressure, lung sounds, palpable pulses). The manikin's head contains a speaker so that the participant can converse with the 'patient' when contextually appropriate. The manikin responds to clinical interventions just as a patient would. Thus, participants interact with a realistic cognitive and physical representation of the full acute care environment and thereby experiences emotional and physiologic responses similar to those experienced in real situations.

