#### APPROACH:

#### **RESEARCH DESIGN AND METHODS:**

**Study design:** High-fidelity simulation experiments performed using three transmissionbased precaution scenarios.

**Study eligibility:** HCP will be recruited for participation in the experimental assessments. The target sample size is 150 subjects with an explicit goal for a diversity of HCP types (i.e. physicians, nurses, and house staff). Eligible subjects must be currently working in a healthcare setting. Because the intricacies of EVD-specific precautions, for the scenarios focused on this type of precautions, volunteers will be recruited from members of the Vanderbilt Communicable Disease Response Team (CDRT). The CDRT consists of HCP from the following disciplines: nurses, physicians (including Epicenter Investigators [name] and [name]), paramedics, and educators. Each team member possesses knowledge and/or skills necessary to care for patients who require intensive medical care. Each volunteer also receives intensive periodic (quarterly) training in the care of patients with highly communicable, serious infectious diseases. Training includes specific disease pathology, PPE use, and EVD infection prevention protocols. Participants will be paid for participation in this study.

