#### Study outcomes and assessment:

1) Lapses in PPE use: These will be captured via video monitoring and recording of each subject experiment from PPE donning through PPE doffing. Two independent investigators will review every scenario and note the frequency and type of breaches in the use of PPE. Investigators will be trained on a standardized method for reviewing each scenario and will use a standardized abstraction tool. The time of the lapse in relation to scenario start will be captured to examine the impact of the duration of PPE use.

2) HCP and environmental contamination: Contamination will be assessed using ultraviolet light inspection of the subjects following doffing of PPE and of the simulation room environment to assess for the number of contamination events during each scenario. The rooms will be cleaned prior to each experiment to avoid cross-contamination.

**Analysis:** A descriptive analysis of the frequency (number per minute of scenario time), number, and types of lapses in PPE use will be performed. The number of self and environmental contamination events (defined as an identified patch of fluorescent powder located in these areas) will also be described as a quantitative number and an event rate per minute of scenario time. Lapse and contamination rates will be compared between each scenario type (Contact, Droplet, and EVD), scenario duration (standard vs. prolonged), and HCP type (physician, nurse, other) using Student's t-test or Wilcoxon Rank Sum test (for duration comparison) and ANOVA or Kruskal-Wallis analysis (for precaution type and HCP type comparison given >2 study groups). For categorical outcomes (e.g. the number of lapses) Fisher's Exact Test will used for comparisons.

**Limitations:** Even with a larger study cohort, the sample size will limit the ability to examine nuanced details in patient care while wearing PPE that lead to lapses. Nonetheless, this will be one of the largest and most complex simulation experiments on PPE use published to date.

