## Specific Aim II: To evaluate in a variety of clinical care settings the effectiveness of a standardized PPE compliance auditing tool coupled with a tiered accountability framework.

**SIGNIFICANCE:** The lessons learned from hand hygiene improvement programs may be helpful when examining methods to audit and improve PPE compliance among HCP. Various innovative interventions to facilitate hand hygiene compliance have been developed over the past decade. These include visible and tactile monitors that alert the HCP to perform hand hygiene in real-time, user-friendly alcohol-based hand rub dispensers that provide easy access to hand hygiene materials, and enhanced monitoring tools. These interventions not only incorporate the practice of hand hygiene into the workflow of HCP but also explicitly emphasize the importance of performing this essential infection prevention practice. Nonetheless, even with advancements in hand hygiene is ultimately rooted in the behavior of the HCP, failure to develop interventions to drive expected behaviors will reduce the impact of these tools. PPE compliance is very similar, as even with advances in the PPE that may facilitate donning, use, and doffing, the underlying determinant of safe PPE utilization is rooted in HCP behavior.

Hand hygiene compliance monitoring has now become a central part of infection prevention programs at most healthcare facilities, and these data are being used on a large-scale as measures of healthcare quality. In Australia, for example, the creation of the National Hand Hygiene Initiative in 2009 required the reporting of hand hygiene compliance in all Australian hospitals using a standardized methodology. The development of a standardized measurement and education process for hand hygiene, the "Five Moments for Hand Hygiene" developed by the WHO, was a major advancement that provided healthcare facilities with a set of tools to improve hand hygiene compliance. In contrast, standardized tools for auditing PPE compliance akin to the "Five Moments" methodology are absent. Ideally, these tools should be guided by data on practices that increase the risk for PPE breaches and the associated contamination of HCP and the environment.

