#### APPROACH:

#### **RESEARCH DESIGN AND METHODS:**

**Study Design:** 1) Audit tool development and field testing; 2) Prospective quasiexperimental phased implementation study.

**Tool Development and Initial Evaluation:** For this Aim, we will first develop a PPE compliance audit tool based on learnings from the simulation experiments in Aim I. Information on the types of breaches in PPE use and the practices that led to these breaches will inform the tool. A review panel of experts in infection prevention, PPE use, and occupational infection prevention (consisting of some members of the Advisory and Steering Committee) will independently review the tool for content validity. An initial evaluation of the tool will then occur as members of the Vanderbilt Epicenter team will perform direct observation of practices using the tool. These observations will occur in a variety of healthcare facility types (including adult inpatient units at a tertiary academic medical center and at a community-based hospital, pediatric inpatient units, outpatient hemodialysis units, and an inpatient rehabilitation hospital). Feedback from these pilot observations, including time to complete and ease of use, will lead to revision of the tool for the second part of this Aim.

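### Aim I seeks risk factors for self-contamination, but its stated analysis never relates the lapses seen in a run to the contamination found in that run

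*Protocol*

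**What the plan says.** The protocol's Specific Aims section states the purpose of Aim I as "To examine risk factors for HCP self-contamination with the donning, use, and doffing of PPE" for three kinds of precautions. The end of the Aim I Significance text puts the goal somewhat differently: "to assess the frequency of and risk factors for PPE breaches using a larger study population". On size, the Aim I methods say "The target sample size is 150 subjects with an explicit goal for a diversity of HCP types"; no power, alpha or effect size accompanies this.

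Under Study outcomes and assessment there are two outcomes. For lapses, two investigators review the video of each experiment, from donning to doffing, and "note the frequency and type of breaches in the use of PPE"; the time of each lapse is kept in order to study duration of PPE use. For contamination, subjects and room are inspected under ultraviolet light after doffing, and patches are counted.

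The Analysis paragraph describes each outcome and then specifies: "Lapse and contamination rates will be compared between each scenario type (Contact, Droplet, and EVD), scenario duration (standard vs. prolonged), and HCP type". The tests named are two-group tests for duration, ANOVA or Kruskal-Wallis for precaution type and HCP type, and Fisher's exact test for categorical outcomes.

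Aim II depends on these results. Its Significance section says of audit tools: "Ideally, these tools should be guided by data on practices that increase the risk for PPE breaches and the associated contamination of HCP" (the sentence goes on to include the environment). Its tool-development paragraph says: "Information on the types of breaches in PPE use and the practices that led to these breaches will inform the tool".

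**The concern.** Lapses and contamination are handled as two parallel outcomes. Each is tabulated against features of the run (precaution type, length) and of the person (HCP type), and neither is set against the other. The analysis can therefore show that one precaution type or profession has more patches than another. It does not ask whether people who make a particular kind of error, or more errors, are the ones who end up contaminated. That is the behavioural part of the objective, and donning, use and doffing are behaviours.

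The matter is not picked up later. Aim II's stated outcome is overall compliance with PPE use, and no contamination is measured there. Aim I is the only place in the programme where lapses and contamination are recorded together. If the link is not examined there, the audit tool will be built without evidence on which audited items go with contamination, which the Aim II background describes as the ideal basis for such a tool.

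**Working it through.** **Objective against analysis.** There is no stated figure to reproduce, so the first step is a comparison of the text.

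| Element | What Aim I fixes |
|---|---|
| Objective | Risk factors for self-contamination |
| Recorded per run | Lapse type, number and time; patches on subject and in room |
| Lapses analysed by | Scenario type, duration, HCP type |
| Contamination analysed by | Scenario type, duration, HCP type |
| Lapse time used for | Effect of duration of PPE use |
| Fisher's exact test used for | Categorical outcomes, with number of lapses as the example |
| Contamination analysed by lapse | Not stated |

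The Limitations paragraph does not fill the gap. It concerns details of care that give rise to lapses, not which lapses go with contamination.

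**What form the exposure must take.** In the 10-volunteer simulation study cited in the Aim I Significance section, all 10 had at least one breach and 80% were contaminated. Cross-classified by any lapse (yes/no), that is 8 of 10 contaminated among those with a lapse and nobody without one. There is no comparison group. If Aim I looks similar, the exposure has to be lapse type or lapse count.

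**Would 150 subjects support such an analysis?** This is an illustration under my assumptions: one record per subject, two-sided alpha 0.05, 80% power, and a share e of subjects committing a given lapse type. With n0 = 150(1 − e), n1 = 150e, contamination risks p0 and p1, and pooled risk p̄:

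power = Φ{ [(p1 − p0) − 1.96·√(p̄(1 − p̄)(1/n0 + 1/n1))] / √(p0(1 − p0)/n0 + p1(1 − p1)/n1) }

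Smallest p1 reaching 80% power:

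| e | p0 = 0.30 | p0 = 0.50 | p0 = 0.60 |
|---|---|---|---|
| 0.25 | 0.556 | 0.755 | 0.839 |
| 0.50 | 0.524 | 0.722 | 0.808 |
| 0.70 | 0.545 | 0.738 | 0.820 |

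The differences p1 − p0 run from 0.808 − 0.60 = 0.208 to 0.556 − 0.30 = 0.256, or about 21 to 26 percentage points.

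For lapse count against patch count, the detectable correlation is r = tanh[(1.960 + 0.842)/√(n − 3)]. With n = 150 this is tanh(2.802/12.12) = 0.23. With n = 75 it is tanh(2.802/8.49) = 0.32.

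These figures ignore multiplicity across lapse types. They also ignore clustering: volunteers outside the Communicable Disease Response Team (CDRT) do both the Contact and the Droplet scenarios (A to D in Table 2), so each contributes more than one run.

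**The case against.** The strongest reply is that the paragraph omits an analysis without excluding it, and that a model with subject effects is often left to a statistical analysis plan, which is not at hand. That holds for the details of the model. It does not cover the choice of question: the protocol names the outcomes, the comparison factors and the tests, and the lapse-to-contamination question is not among them. If an analysis plan already contains it, the protocol only needs to be brought into line.

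A second reply is that the objective is already served. Precaution type, duration and HCP type are genuine candidate risk factors, contamination is compared on all three, and the protocol also words the goal as risk factors for breaches. This stands in part and narrows the point to behaviour as a risk factor. A reader might infer that Aim I can identify no risk factor at all; that would be wrong.

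A third reply concerns the evidence. A reader might take the cited gloving study as proof that error frequency misleads: errors were similar ("72% with any error in double gloving scenarios; 67% in the single gloving scenario") while hand contamination was 28% against 78%. It cannot carry that weight. The 18 volunteers were compared under different PPE, so the second glove layer may explain the gap. The errors are pooled over types and are not linked to contamination within a person.

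Nor do the documents say that the Aim II tool will be weighted by how common a lapse is. It draws on breach types and the practices behind them, followed by expert review and piloting, and the sentence about contamination is background that begins with a qualifier. What stands is that no planned result would supply the association.

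**Conclusion.** The point holds in limited form. The stated Aim I analysis addresses some candidate risk factors for self-contamination, but does not examine whether observed lapses are associated with it, although both are recorded in every run and nothing later in the protocol links them.

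The consequence cannot be sized from the documents. The illustration shows only that, with 150 subjects and a lapse type that is neither rare nor universal, a difference of roughly 21 to 26 percentage points would be detectable under the simplifications stated. Smaller effects and rare lapse types would not be settled.

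A reader might want the analysis to show which lapses cause contamination. The design does not allow that. Inspection takes place once, after doffing, so a patch cannot be dated to a particular lapse. Association within a run is the most that can be claimed.

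**What to change.** In the Aim I Analysis paragraph, add a prespecified per-run analysis with contamination of the subject as the dependent variable, kept separate from patches in the room. The explanatory variables are lapse type or lapse count, grouped by phase (donning, in-room use, doffing). Adjust for scenario, duration and HCP type, and use a random effect for subject or GEE, because non-CDRT volunteers complete several scenarios. Avoid an any-lapse indicator, since nearly everyone may have one. State that results are associations.

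In the Aim II tool-development paragraph, say that these associations will inform the choice of audit items alongside the types of breach observed.

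The cost is a few sentences and some extra analysis. The lapses and subject patches are already to be recorded, and phase can be coded from video that already runs from donning to doffing. Body-site or under-clothing detail is not stated as recorded, so the analysis should not depend on it unless it is in fact collected. Rare lapse types will have wide intervals and need to be grouped.

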## Study procedures:

Three transmissionbased precaution scenarios will be utilized (Table 2). These will involve Contact Precautions (PPE: gown and gloves), Droplet Precautions (PPE: surgical mask), and EVD-Precautions (PPE: PAPR, eve protection, hood, aown. double aloves. lea

coverings, and apron). For the Contact Precautions scenario, subjects will perform a brief history and abbreviated physical exam along with a simulated wound dressing change. For the Droplet Precautions scenario, subjects will perform a brief history and abbreviated physical examination along with management of a urinary catheter (including emptying of collection bag). For the EVD-Precautions scenario, subjects will perform a brief history and abbreviated physical exam along with medication administration through an intravenous catheter. Non-CDRT personnel will participate in both the Contact and Droplet scenarios (A-D in Table 2), while only CDRT members will participate in the EVD-Precautions scenario (E & F in Table 2). Each

scenario will have a standard 10 minute duration and a prolonged 20 minute duration (in which the exam is a standard physical exam) to assess the impact of prolonged PPE use on compliance.

Using a fluorescent compound to reproduce contaminants in assessing

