#### Table 2: Simulation Scenarios for Aim I

Scenario	Standard Duration (10 mins)	Prolonged Duration (20 mins)				
Contact Precautions	Α	В				
Droplet Precautions	С	D				
EVD-Precautions	E	F				

contamination rate is effective and can be utilized for comparison with body and environmental contamination levels. A fluorescent powder (Glo Germ Co, Moab, UT) especially developed for determining hand hygiene compliance will be used in this study. The powder will be applied in standardized amounts at locations surrounding and on the simulated patient (on patient's upper torso and arms, within the simulated wound for scenarios A & B, on the urinary collection bag for scenarios C & D, on the peripheral IV hub in scenarios E & F, on both bed rails, and on the patient's bedside table) prior to the scenario start. Subjects will be blinded to the locations of powder placement.

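### Aim I tests contamination across Contact, Droplet and EVD scenarios that differ in PPE coverage, task and powder site, so a difference cannot be attributed to PPE technique.

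*Protocol*

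**What the plan says.** All of this is in the Protocol, Specific Aim I.

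- **PPE.** Study procedures lists "Contact Precautions (PPE: gown and gloves") and "Droplet Precautions (PPE: surgical mask"). The EVD scenario has a full ensemble that includes a powered respirator, hood, gown, double gloves, apron and leg coverings. Table 1 likewise shows neither gloves nor gown for Droplet.
- **Task.** Every scenario includes a history and a hands-on examination. Contact adds a dressing change ("abbreviated physical exam along with a simulated wound dressing change"). Droplet adds "management of a urinary catheter (including emptying of collection bag"). EVD adds intravenous medication.
- **Powder.** Sites common to all scenarios are "on patient's upper torso and arms" and "on both bed rails, and on the patient's bedside table". The task-specific site is the wound in A and B, "on the urinary collection bag for scenarios C & D", and the IV hub in E and F.
- **Event.** Ultraviolet inspection follows PPE removal. Any patch of powder on the subject or in the room counts. It need not lie on a site that the PPE covers or follow an observed breach.
- **Comparison.** "Lapse and contamination rates will be compared between each scenario type (Contact, Droplet, and EVD"), by ANOVA or Kruskal-Wallis. Duration and HCP type (physician, nurse, other) are listed as further comparisons, with no mention of precaution type as a stratum.
- **Subjects.** Non-CDRT staff do both Contact and Droplet. Only CDRT members do EVD.
- **Limitations.** The paragraph mentions sample size only.

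**The concern.** Aim I is about risk factors for self-contamination that arise from handling PPE. A test across precaution types serves that purpose only if the tracer count responds mainly to how the PPE was handled. Here it also responds to how much skin and clothing the scenario leaves uncovered, to what the subject was asked to touch, and to where powder was placed. A significant result could be reported as one precaution type being used less safely than another when the technique was equally good in both.

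The same mixing can reach the HCP-type comparison. If the professions are spread unevenly over Contact, Droplet and EVD sessions, a pooled comparison of professions carries the coverage differences with it.

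**Working it through.** Aim I states a target of 150 subjects but no power, effect size or standard deviation, so there is no figure of the plan to reproduce. The check is mainly a reading of the sections side by side.

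**Step 1. What a Droplet subject can pick up without a PPE error.** The examination brings hands and sleeves to powdered torso and arms, and emptying the bag brings hands to a powdered object. The listed mask covers none of the skin or clothing involved. Powder found on hands or sleeves is then an event under the protocol's definition, although nothing went wrong with the mask.

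**Step 2. The same contacts in Contact.** Hands and sleeves meet the same common sites, but through gloves and a gown that are removed before inspection. Powder remaining on the subject has passed or bypassed a barrier.

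**Step 3. What varies with precaution type.** Three things change together: coverage, task and task-specific powder site. For EVD the people change too, since CDRT members receive quarterly PPE training. The count alone cannot separate these from technique.

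**Step 4. Could this reach significance?** The following is an illustration with assumed values, not a prediction. It uses the proportion of subjects with any powder, two independent groups of n and two-sided 0.05.

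- Contact rate p1: 0.80, borrowed from the cited ten-volunteer powder simulation with gown, gloves and N95, or 0.90 as an alternative assumption.
- Droplet rate p2: assumed 0.95 to 0.99, with no mask error.
- Power = Φ[(|p2 − p1| − 1.96·se0)/se1], where se0 = √(2·p̄(1 − p̄)/n), se1 = √([p1(1 − p1) + p2(1 − p2)]/n) and p̄ = (p1 + p2)/2.

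For p1 = 0.80, p2 = 0.95, n = 100: p̄ = 0.875, se0 = √(2 × 0.875 × 0.125/100) = 0.0468 and se1 = √((0.16 + 0.0475)/100) = 0.0456. Then (0.15 − 0.0917)/0.0456 = 1.28, and power is 0.90.

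| n per scenario | Contact rate | Power, Droplet 0.95 | Power, Droplet 0.99 |
|---|---|---|---|
| 50 | 0.80 | 0.62 | 0.89 |
| 100 | 0.80 | 0.90 | 0.995 |
| 50 | 0.90 | 0.16 | 0.51 |
| 100 | 0.90 | 0.27 | 0.80 |

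A significant difference with no mask failure is possible, and whether it is likely depends heavily on the Contact rate. The planned analysis uses event counts and rates, and the same people do Contact and Droplet, so the table shows only that the problem is not negligible.

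**Step 5. HCP type and duration.** Study eligibility describes the CDRT as nurses, physicians, paramedics and educators, whereas the general recruitment goal names physicians, nurses and house staff. The category of other HCP could therefore be weighted towards EVD sessions, and a pooled HCP-type comparison would then mix profession with coverage. Duration differs: Table 2 gives each precaution type both a 10-minute and a 20-minute version, so duration is crossed with type.

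**The case against.** The strongest reply is that the mask-only reading is an inference. The Significance section says transmission-based precautions are added to Standard Precautions, which apply to every patient and cover body fluids and excretions. Subjects might therefore glove to empty a urine bag. This stands in part: the protocol neither requires nor excludes gloves in C and D. But it does not standardise them there either, and voluntary gloving would add uncontrolled variation without making the scenarios comparable.

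Three stronger readings are tempting, and the documents do not support them.

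- **That Droplet must rank worst.** The cited simulations already report high contamination in subjects wearing gown and gloves: 80% of subjects in one, and hands 70–90% and clothing 75–100% in another. The outcome also includes room contamination, and powder sites differ. A higher Droplet count on hands is plausible, but the overall ranking and its size are not shown. The cited 28% versus 78% compares double with single gloves using a bacteriophage, so it does not supply the size for bare hands and powder.
- **That Droplet counts say nothing about PPE.** Powder carried by hand to the mask or face during wear or removal is a genuine PPE event. Cited work lists touching the face with contaminated gloves as a breach.
- **That a distorted ranking would drive the Aim II audit tool.** Tool Development says the tool draws on the types of breach and the practices behind them. It mentions no ranking of precaution types by contamination.

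It can also be said that stratification belongs in an SAP. That would answer an omission. Here the protocol itself fixes the event definition, the cross-type comparison and the tests.

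**Conclusion.** The point holds as a matter of interpretation. A cross-type difference in self-contamination reflects coverage, task and powder site as well as technique, so it cannot be attributed to the handling of PPE, and Limitations does not say so. Neither direction nor size is fixed in advance. The illustrative power of 0.16 to 0.995 over n = 50 to 100 rests on assumed contamination rates and independent groups.

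The pooled HCP-type comparison is open to the same confounding if professions are unevenly spread between EVD and the other scenarios. The duration comparison is less affected, because both durations exist for each type.

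Descriptive contamination rates within a scenario are not touched. Nor is the lapse outcome as a measure of PPE use, although the number of items that can be mishandled differs between scenarios.

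**What to change.** In the Analysis paragraph of Aim I:

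1. Make the HCP-type and duration comparisons of contamination within precaution type, or stratified by it.
2. Report contamination across precaution types descriptively, or limit the formal test to contamination events linked to a breach seen on video.

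In Limitations, state that cross-type contrasts reflect coverage, task and powder site as well as PPE technique.

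Two other repairs look attractive but bring comparability problems of their own. Testing only lapses across types sets a single mask against ensembles with more opportunities for error. Scoring the face for Droplet against hands, arms and torso for Contact compares different body zones and needs the site of each patch recorded.

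Cost: the formal cross-type test of total contamination is given up, and within-type comparisons are somewhat less precise. The descriptive route needs only wording. The breach-linked route also needs patches to be matched to the video review, and differing opportunity for error would still call for caution.
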